Patients will be referred by the Spectrum Health breast surgeons. If the patient is interested, the investigator or research staff will provide a copy of the informed consent for the patient to review. Spectrum Health research staff will then follow up with the patients to further discuss the study and confirm that the patient is interested in participation.

Patients will then be consented by a clinical research coordinator. Typically, this would occur at the hospital where they will be undergoing their surgery. The coordinator will review the consent with the patient (and family or significant other, as applicable) and have the patient sign it. The coordinator will make all reasonable attempts to keep the discussion as private as possible. In order to minimize coercion, it will be made very clear to patients that their participation is strictly voluntary and that not choosing to participate will in no way affect their present or future care at Spectrum Health.

Once the patient has been randomized to either PEC or PVB, the anesthesiologist on call for local blocks will see the patient and review that analgesic plan and the risks of that specific procedure with the patient. This meeting and explanation are standard, but they may also answer questions the patient may have related to the study.

We anticipate enrolling 128 total patients in the study, 64 in the PVB arm and 64 in the PEC arm.

There will be no payment to patients for inclusion in the study.

b. Inclusion and Exclusion Criteria

Inclusion Criteria:

- i. Female patients \geq 18 years of age
- ii. Total mastectomy or partial mastectomy with or without reconstruction OR planned lumpectomy.
- iii. Patient determined by their surgeon as medically able to receive a regional block for post-operative analgesia
- iv. Patient agrees to participate in the study and signs informed consent

Exclusion Criteria:

- i. Neoadjuvant radiation therapy
- ii. Stage IV cancer
- iii. Planned general anesthesia use during surgery
- iv. Allergies to ropivacaine, midazolam, fentanyl, or propofol
- v. Pregnant women
- vi. Prisoners
- vii. Adults unable to consent
- viii. Non-English-speaking patients

c. Study Endpoints

Primary Outcome Variables:

Intraoperative narcotic use, Post Anesthesia Care Unit (PACU) narcotic use and postoperative narcotic use. We would expect that all variables will have a lower values in patients randomized to PEC versus PVB.

Secondary Outcome Variable(s):

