Length of operation, estimated blood loss, incidence of postoperative nausea, subjective pain at two weeks (including patient's overall pain rating for the previous two weeks, the patient's stated last time they used pain pills) and number of calls to physician's office following hospital discharge.

d. Procedures Involved in the Research

This is a prospective, randomized study.

Following satisfaction of the inclusion/exclusion criteria and signed informed consent, patients will be randomized to paravertebral block or a pectoral nerve block. The randomization schedule will be set-up prior to study start using an Excel spreadsheet. Spectrum Health statisticians designed the randomization schedule to meet significance for the endpoints. Randomization is 1:1, PEC:PVB. If the patient is unwilling to be randomized to one or the other type of block, they will not be able to participate in the study. After each patient is consented, the randomization schedule will be checked and the data sheet with the type of block to be used will be placed in

the patient chart. The research coordinator will notify anesthesia of which block will be used on the patient.

Patients will proceed to surgery per usual standard of care. The PVB is performed along the spine utilizing ultrasound guided technique. The PEC is performed anteriorly, at the level of the axillary line, also utilizing ultrasound guided technique. Each block will be performed using 20-30 mL 0.5% Ropivacaine¹ per side. Midazolam and fentanyl will be used for sedation as needed. Intraoperatively, patients will undergo monitored anesthesia care with a propofol infusion (50-150 mcg/kg/min). Additional IV fentanyl will be given as needed. Anesthesia will be converted to general anesthesia if the patient is unable to tolerate the procedure with sedation and block anesthetic or if general anesthesia is preferred by the surgeon. This will not disqualify the patient, but the conversion will be noted in REDCap.

¹Package inserts for these FDA-approved drugs are included as Appendix A to the protocol.

All post-operative care will be standard of care.

Data collected will include the following:

- i. Demographics¹
- ii. Medical history²
- iii. Surgical procedure performed & pain control technique(s) used
- iv. Extra doses of narcotic and sedative medication used during surgery.³
- v. Length of surgery
- vi. Duration of hospital stay (measured in minutes)

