- vii. Total of extra narcotic and sedative medication used while in PACU and in the first 24 hours post-PACU (or until discharge, whichever comes first)
- viii. Total doses of anti-nausea medication used while in PACU and in the first 24 hours post-PACU (or until discharge, whichever comes first).
- ix. Which anesthesiologist performed the procedure
- x. Two-week post-operative visit pain rating (subjective information from the patient about their over-all pain rating for the previous two weeks, as well as the approximate last time they used pain pills)
- xi. Number of phone calls to the surgeon's office for concerns about pain in the time post-discharge and prior to the office visit.

¹Include distance the patient lives from the Lemmen-Holton Cancer Pavilion, their self-reported ethnicity and age.

²Include stage of tumor, outpatient chronic use of narcotics, diagnosis of chronic pain, ASA classification, current diagnosis, major comorbidities and BMI.

³Defined as total amount of narcotic/sedative medication given during surgery, in milligrams,

Standard of care follow-up will occur at 2 weeks with the physician who performed the surgery. Patient will be asked about pain pill use; those units will be converted to morphine equivalents. This information may also be obtained through a phone call.

This trial is registered on clinicaltrials.gov

Schedule of Events:

Study Requirements	Pre-Surgery Visit	Day of Surgery	PACU	1 st 24 hrs. post-surgery	Post-Surgery Visit (2 wks after surgery, +/- 1 week) ³
--------------------	-------------------	----------------	------	--------------------------------------	---

Eligibility Criteria	X				
Consent	X¹	X			
Randomization		X			
Surgery, using PEC or PVB		X			
Data Collection ²		X	X	X	X
Adverse Events		X	X	X	X

¹ Consent may be done either prior to the day of surgery or on the day of surgery, depending on timing and patient preference.

² Includes patient demographics, medical history, block procedure used (PVB or PEC), method of pain control used during surgery, extra narcotic/sedative use during surgery, length of surgery, extra narcotic and sedative use in PACU, name/total dosage of narcotic use during post-op hospitalization, duration of hospitalization

³ Data collected from this time period may be done over the phone as well as at the surgeon's office.

e. Data Management

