The study investigators (Spectrum Health Breast Surgeons) will introduce the study to the patients at their pre-surgery visit. They will fill out and sign an eligibility checklist for the research coordinators. The research coordinators will then reach out to the patient to confirm interest in the study and will give the patient a copy of the informed consent, if they have not already received one. The coordinator will then review the consent with the patient and family (as applicable). Adequate time will be allotted for the patient and/or family and friends to ask questions. Enough time will also be allowed for both the patient and the coordinator to feel that there is an adequate understanding of the study and the responsibilities involved. Subjects will be informed that the research study is voluntary. If the patient is still interested, they will sign a copy of the research consent. A copy of the consent will be given to the patient and a copy will be placed in their medical chart. On the morning of surgery, when the anesthesiologist comes in to discuss anesthesia and pain control with the patient, he or she will also discuss the research study with the patient.

17. Vulnerable Populations:

This study will not include any vulnerable populations.

18. *Sharing of Results with Subjects:*

There are no plans to share study results with the research subjects.

19. References:

1. Glissmeyer, Johnson, Sherman, et al. Effect of paravertebral nerve block on narcotic use after mastectomy. *American Journal of Surgery*. 2015. article in press
2. Wahba, Kamal. Thoracic paravertebral block versus pectoral nerve block for analgesia after breast surgery. *Egyptian Journal of Anaesthesia*. 30.129-135. 2014.
3. Sopena-Zubiria, Fernandez-Mere, Arias, et al. Thoracic paravertebral block compared to thoracic paravertebral block plus pectoral nerve block in reconstructive breast surgery. *Revista Espanol De Anestesiologia Y Reanimacion*. 2012 Jan; 59(1): 12-7
4. Bashandy, Abbas. Pectoral nerves I and II blocks in multimodal analgesia for breast cancer surgery: a randomized clinical trial. *Regional Anesthesia and Pain Medicine*. 2015 Jan; 40(1): 68-74

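### The two-week pain rating and last pain-pill use are gathered around a visit with an unmasked surgeon-investigator, or by phone, and the protocol does not fix who asks, how, or whether the mode is recorded.

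*Combined protocol and SAP*

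**What the plan says.** Section 8d (Procedures Involved in the Research) sets the contact: "Standard of care follow-up will occur at 2 weeks with the physician who performed the surgery". The list of collected data in that section describes the two-week pain item as "subjective information from the patient about their over-all pain rating for the previous two weeks", together with the approximate time pain pills were last used. Section 8c lists both among the secondary outcomes. On medication, 8d adds: "Patient will be asked about pain pill use; those units will be converted to morphine equivalents". The person asking is not named.

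The mode is open. The text of 8d allows a phone call, and footnote 3 to the Schedule of Events repeats it: "Data collected from this time period may be done over the phone", with the surgeon's office as the other route. No rule says which patients are phoned or by whom, and the mode of contact is not among the data items listed in 8d.

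Three other places bear on who knows the allocation and who has an interest in the result:

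- Section 16 (Consent Process): "The study investigators (Spectrum Health Breast Surgeons) will introduce the study to the patients at their pre-surgery visit".
- Section 8d, on randomization and what goes into each patient's chart: "the data sheet with the type of block to be used will be placed in".
- The recruitment text before Section 8b, on what follows randomization: "the anesthesiologist on call for local blocks will see the patient and review that analgesic plan and the risks of that specific procedure".

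The available text describes no masking of patient, surgeon, anesthesiologist or coordinator, and no independent assessor. Section 9b plans t-tests and chi-square tests, with no allowance for mode of collection.

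**The concern.** An answer about pain over the past two weeks can depend on who asks, how the question is put, and whether the patient is answering her own surgeon. If the person asking knows the block and has a stake in the result, that influence need not be equal in the two arms.

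The two-week rating is the only direct pain score among the listed endpoints. The primary variables are narcotic use, which is a proxy for pain. Section 4 aims to show that the two blocks relieve pain equally, so readers will look to the rating to judge whether any narcotic result came with acceptable pain. For such a question an arm-related shift does harm in either direction: it can produce a difference that is not there or hide one that is.

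**Working it through.** **1. The plan's own figure.** Section 9a takes a PVB mean twice the PEC mean and an SD equal to the PVB mean. With PVB mean m, the difference is m − m/2 = 0.5m and the SD is m, so the standardized effect is d = 0.5. With alpha 0.05 two-sided and power 0.80:

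n per arm = 2 × (1.960 + 0.842)² / 0.5² = 62.8, so 63 by the normal approximation.

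The exact two-sample t-test gives 63.77, so 64, with power 0.801 at 64 per arm. This matches the stated 64. A one-sided test would give 50, so the plan's figure is two-sided. It concerns 24-hour narcotic use. No design figure is given for the two-week outcomes, and 64 per arm is used below only as the planned number of patients.

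**2. Assessor route.** Suppose there is no true difference and questioning shifts one arm by b SD relative to the other. The t statistic then has noncentrality b × √(64/2) = 5.657b on 126 degrees of freedom. The values of b are assumptions; the documents give none.

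| Assumed shift b (SD) | Noncentrality | Rejection rate at two-sided 5% |
|---|---|---|
| 0 | 0 | 5.0% |
| 0.1 | 0.566 | 8.7% |
| 0.2 | 1.131 | 20.2% |
| 0.3 | 1.697 | 39.1% |

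Normal check at b = 0.2: 1.960 − 1.131 = 0.829, upper tail 0.204, lower tail 0.001, total 0.205, against 0.202 from the exact calculation.

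The same numbers show the opposite harm. If the true difference were 0.5 SD and questioning moved it by 0.2 SD towards zero, the test would see 0.3 SD. The chance of detecting the difference would fall from 80.1% to 39.1%.

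**3. Mode route.** If phone answers differ from office answers by s SD and the phone share differs between arms by Δp, the spurious shift is s × Δp. With s = 0.5 assumed:

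| Difference in phone share | Shift (SD) | Rejection rate |
|---|---|---|
| 0 points | 0 | 5.0% |
| 10 points | 0.05 | 5.9% |
| 20 points | 0.10 | 8.7% |
| 30 points | 0.15 | 13.4% |

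With s = 0.2, a 30-point imbalance gives 6.3%. When phone use is equal in the two arms and mode does not interact with arm, the comparison is not biased; there is only extra variance, s² × p(1 − p) for phone share p. This is largest at p = 0.5: 0.25 × 0.25 = 0.0625, so the SD rises by a factor √1.0625 = 1.031, about 3%.

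**4. What the text establishes.** The visit is with the operating surgeon (8d). The breast surgeons are investigators (16). The block is on a sheet in the chart (8d). Phone is an alternative with no rule (8d). These facts make it possible that an unmasked, interested person asks the question. They do not establish that it happens, or in which patients.

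**The case against.** The strongest reply is that the documents leave the asker open. The sentence on pain pills is passive, and Section 8e has research staff managing the data, so a nurse or coordinator might ask at the visit. A reader might infer that the surgeon personally takes the rating; the text does not say so. This stands. The remaining defect is that the protocol assigns nobody and excludes nobody.

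A reader might also take the statement in Section 8c, "We would expect that all variables will have a lower values in patients randomized to PEC versus PVB", as a prediction of less two-week pain with PEC. It stands under the primary outcome heading, directly after the three narcotic-use variables and before the secondary outcomes, while Sections 4 and 11 speak of equal pain relief. It shows that the investigators hold an expectation about narcotic use. It is not a hypothesis about the pain rating.

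Mixed mode is not bias in itself. Nothing in the documents suggests that phone use will differ by arm, and step 3 shows a modest effect even with a 20-point imbalance. This stands too, although nothing in the plan would prevent or detect an imbalance.

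Larger shifts can be tabulated: 0.4 SD gives 61.2%. On a rating with an assumed SD of 2.5 that is 0.4 × 2.5 = 1 full point across a whole arm, and the documents give no ground for thinking that questioning alone could do this.

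Two further points stand. The patient is told her block and rates her own pain, so her own expectation is at least as direct a route to bias as the questioner. And Appendix B (the REDCap forms) and part of the protocol text were not available for review, so a scale, a script or a mode field may exist there.

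**Conclusion.** The point holds as a gap in how two secondary outcomes are collected. The two-week pain rating and last pain-pill use are gathered around a visit with an investigator who can know the block, or by phone, with the asker, the choice of mode and its recording all left open.

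Its size cannot be derived from the documents. The rates of about 9%, 20% and 39% rest on assumed shifts of 0.1, 0.2 and 0.3 SD, complete data on 64 per arm, and a two-sided t-test. They show how sensitive the comparison is and do not estimate the bias in this trial.

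A reader might infer that the primary result is compromised. The documents do not support that: Section 9a defines the primary variable as narcotic use in the first 24 hours, which is not collected at this visit. Section 8c lists postoperative narcotic use without a time limit, but 9a supplies one. The change is worth making because it is cheap; the trial's main comparison does not depend on it.

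**What to change.** Amend Section 8d to say that every patient records the overall pain rating and the date of her last pain pill herself, on a one-page form or a REDCap survey, before she sees the surgeon. A call with a fixed script is used only for patients who do not respond. The mode is recorded for each patient, so that its balance between arms can be reported. The surgeon neither asks for nor enters these items. The pill use that 8d converts to morphine equivalents can go on the same form.

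Self-completion is preferable to relying on a masked interviewer, because the coordinators consult the randomization schedule and tell anesthesia which block to use.

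The cost is one form or survey in a system the trial already uses (Section 13), a few sentences in 8d, and some staff time to issue forms, chase incomplete ones and make the scripted calls. Treatment, visits and sample size do not change. Because patients know their block, the change reduces the bias and does not remove it; the report should say so.

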Data to be collected are detailed in Appendix B (pdfs of REDCap database for this study). Data will be managed by Spectrum Health research staff and kept in a locked cabinet or a limited-access electronic drive.

f. Provisions to Monitor the Data for the Safety of Subjects

The Principal Investigator will oversee the safety of the study. This safety monitoring will include careful assessment and appropriate reporting of adverse events (see "Adverse Events" below).

g. Withdrawal of Subjects

A patient may be withdrawn from the study prior to the expected completion of that subject for failure to adhere to protocol requirements. Patients may choose to withdraw from the study at any time. Data that have already been collected on these patients will still be used.

The primary investigator may remove a patient at any time from this research study if it is felt to be in the best interest of the patient.

9. Statistical Plan:

a. Sample Size Determination

The primary outcome variable for this study is the difference in narcotic use between the PEC group and the PVB group during the first 24 hours following surgery. If we define a clinically important effect as the mean narcotic use in the PVB group is twice that seen for the PEC group, with a standard deviation equal to the mean of the PVB group, with $\alpha=0.05$ and $\beta=0.20$, we will be able to detect a statistically significant difference with 64 subjects in each group, using the unpaired t-test. Complication rates will also be compared between the two

groups, although with an anticipated rate of only 5% in the PVB group, it is unlikely with the projected sample size that we will find a statistically significant effect for this variable.

b. Statistical Methods

Summary statistics will be calculated. Quantitative data will be expressed as the mean + SD, while nominal data will be expressed as a percentage. Comparisons between groups for quantitative variables will be performed using the t-test. Nominal variables will be evaluated using the Chi-Square test. The data will be analyzed as intention to treat. Significance will be assessed at $p<0.05$.

10. Risks to Subjects:

Risks of both procedures are very low – less than 5% for each risk listed here.

PEC

- a. Vascular puncture
- b. Inadequate analgesia
- c. Intraneuronal injection, resulting in transient neuropathy
- d. Incomplete nerve block
- e. Infection

PVB

- a. Pneumothorax
- b. Vascular puncture
- c. Incomplete nerve block

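### Section 9b's unadjusted t-test of first-24-hour narcotic use is valid; pre-specified adjustment for planned procedure and chronic narcotic use is an optional, cheap improvement with a modest, conditional gain

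*Combined protocol and SAP*

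**What the plan says.** Section 9a takes narcotic use in the first 24 hours after surgery as the primary outcome. It sizes the trial on an unpaired t-test at alpha 0.05 and beta 0.20, which leads to 64 per arm. The effect to be detected is "mean narcotic use in the PVB group is twice that seen for the PEC group". The spread comes from a second assumption: "with a standard deviation equal to the mean of the PVB group". Section 9b carries the same test into the analysis: "Comparisons between groups for quantitative variables will be performed using the t-test". It names no covariate.

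The inclusion criteria admit "Total mastectomy or partial mastectomy with or without reconstruction OR planned lumpectomy". None of the eight exclusions concerns chronic narcotic use or chronic pain. One exclusion, "Planned general anesthesia use during surgery", may narrow the mix of procedures in practice.

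Under Procedures Involved in the Research, outpatient chronic narcotic use is a medical-history item. For procedure, the listed item is "Surgical procedure performed & pain control technique(s) used", which is the operation carried out, not the one planned. On allocation the same section says "The randomization schedule will be set-up prior to study start using an Excel spreadsheet", at 1:1, and it mentions no stratification factor.

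**The concern.** Extent of surgery and prior narcotic use are plausible sources of between-patient variation in an outcome that is itself narcotic use. An unadjusted comparison leaves that variation in the error term. If the factors are prognostic, the same 128 patients could give a more precise PEC minus PVB difference.

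A second issue is the single realized estimate. If the schedule is unstratified, one arm may by chance receive more of the larger operations. The unadjusted difference would carry that imbalance.

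Naming covariates in advance also avoids choosing them after an imbalance has been seen.

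**Working it through.** **1. The plan's own figure.** Set the PVB mean to 1. Section 9a then gives a PEC mean of 0.5 and an SD of 1, so the standardized effect is (1 - 0.5)/1 = 0.5. The noncentrality at 64 per arm is 0.5 × sqrt(64/2) = 2.83. With 126 df and a two-sided 5% test, power is 80.1%. Solving for 80% power gives 63.8, so 64 per arm. The plan's figure reproduces. Sidedness is not stated, but a one-sided test would need only 51.

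**2. What the covariates could explain.** The documents give no association, prevalence or case mix, so these are assumptions. Let a share p of patients have larger procedures that use r times as much. The share of PVB-arm variance explained is

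R² = p(1-p)(r-1)² / (1 + p(r-1))².

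For p = 0.5 and r = 1.5, 2, 3 this is 0.04, 0.111, 0.25. If the PEC effect is a ratio in every patient group, the PEC-arm slope is half the PVB slope b. One pooled slope is then 0.75b and removes only 0.5625 of that R²: 0.0225, 0.0625, 0.141. If the absolute difference is constant (additive), the full R² is removed.

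**3. Cost when the covariates explain nothing.** Losing 3 df alone leaves power at 80.1%. Chance correlation between arm and three covariates takes about 3/127 = 2.4% of the information on arm. The noncentrality becomes 2.83 × sqrt(1 - 0.024) = 2.79, and power is about 79%.

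**4. Power of the adjusted model by simulation.** The model is a linear regression on arm, two procedure indicators and chronic use (10% prevalence). It uses HC2 standard errors, 64 per arm, marginal SD 1 in both arms and normal errors. There were 40,000 trials per setting, so the simulation error is about sqrt(0.8 × 0.2/40,000) = 0.2 points. Larger procedures were split evenly between the two larger categories.

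| Assumption | Ratio effect | Additive effect |
|---|---|---|
| No association | 79% | 79% |
| Larger procedures 1.5-fold, 50/50 mix | 80-81% | 80-81% |
| Twofold, 50/50 | 81% | 83-84% |
| Threefold, 50/50 | 84% | 89% |
| Procedure and chronic use both twofold, 50/50 | 83% | 87% |
| Twofold, 20% larger procedures | 81% | 84% |
| Threefold, 20% larger procedures | 85% | 92% |

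The t-test stays at about 80% throughout. Type I error is 4.7-5.2% for both the t-test and HC2. HC3 holds 4.3-4.8% and costs about one further point of power, so HC2 is the better default here.

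**5. Precision.** The half-width of the 95% CI is t × sqrt(2(1-R²)/64). It is 0.350, 0.332 and 0.313 of the PVB mean at a removed R² of 0, 0.1 and 0.2.

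**6. Chance imbalance.** With simple allocation and a factor of 50% prevalence, the exact binomial chance that the arms differ by at least 15 points is 0.093. The slope b is 0.667 for r = 2 and 1 for r = 3. A 15-point imbalance shifts the unadjusted estimate as follows, against a target difference of 0.5 SD:
- ratio: 0.15 × 0.75 × b = 0.075 or 0.112 SD
- additive: 0.15 × b = 0.100 or 0.150 SD

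**7. Can the covariates be fixed before allocation?** Chronic narcotic use is history. Eligibility depends on the planned operation, and under Section 16 the surgeon signs an eligibility checklist. The Schedule of Events puts randomization on the day of surgery. Planned procedure is therefore knowable in time. Whether it is stored cannot be seen, because Appendix B (the REDCap forms) is not in the text supplied.

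**The case against.** The strongest case against is that nothing here is wrong. The analysis matches the test used for sizing, and its error rate already allows for chance imbalance on average over randomizations. Every gain rests on assumed use ratios. Section 9a frames the effect as a ratio, and under that framing adjustment loses about a point with no association, is level at 1.5-fold and gains about one point at twofold. Only a threefold ratio gives 4 points. The imbalance argument also requires an unstratified schedule. The schedule was designed by statisticians and is not shown.

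All of this stands, and it is why the point is optional. What remains is a small downside, a possible moderate gain, and protection of the one estimate that the trial will yield.

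A reader might infer a larger gain. Putting R² of 0.10 or 0.20 straight into the power formula gives 84.1% or 88.1%. The documents do not support that reading. They give no R², and the formula ignores both the pooled-slope loss in step 2 and the imbalance cost in step 3. At a twofold ratio the PVB-arm R² is already 0.111, yet simulated power is only about 81% (ratio) or 83-84% (additive).

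**Conclusion.** An optional improvement, to be considered. In the 50/50 scenarios the change in power is about -1 to +4 points with a ratio effect, and up to +9 with an additive effect and a threefold difference. It is close to neutral unless procedure or chronic use is clearly prognostic. These figures rest on assumed use ratios, prevalences and a common marginal SD.

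Three stronger inferences are not supported. The t-test is not invalid or biased for want of covariates, because randomization justifies it. The trial is not undersized on its own assumptions, because 64 per arm reproduces. And adjustment would not by itself enable the trial to demonstrate the equal analgesia named in the primary objective.

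**What to change.** Add to Section 9b, before outcomes are seen:

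> The primary analysis of first-24-hour narcotic use (Section 9a) is a linear regression on randomized arm, adjusted for outpatient chronic narcotic use (yes/no), planned procedure category as recorded before randomization (lumpectomy or partial mastectomy without reconstruction / total mastectomy without reconstruction / any procedure with reconstruction), and any factor used to stratify the schedule. The adjusted PEC minus PVB difference is reported with a 95% CI from HC2 robust standard errors. The unadjusted t-test is a sensitivity analysis. Variables arising after randomization (procedure performed, length of surgery, conversion to general anesthesia) are not covariates. The same model is used for the intraoperative and PACU narcotic outcomes listed under Study Endpoints.

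Cost: one paragraph and one regression with three covariate df, and about 1 point of power if the covariates explain nothing. Planned procedure needs one pre-randomization field if the eligibility checklist or REDCap form does not already hold it. No extra patients or visits are needed.
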